## **9.9 Urinalysis**

Dipstick testing may be performed in the clinic or the lab, as long as the required elements (glucose, protein, and hemoglobin) are tested. The examination is performed on urine obtained by clean catch.

If the screening dipstick is transiently abnormal due to menses or infection, document this issue in the participant's source documentation. For infection, provide appropriate treatment and/or referral. Following resolution, repeat the dipstick.

Follow-up urinalysis should be deferred if a participant is menstruating, but should be performed as soon as possible. If a follow-up dipstick is abnormal due to a participant's menstrual period, document in the comment section of the case report form (CRF) and repeat the dipstick once the participant is no longer menstruating. A micro-urinalysis is not required.

See relevant section of the Ab Manual of Operations (MOP) for further details.

## **9.10 Assessments of Solicited AEs**

For all participants, baseline assessments are performed before and Solicited AE assessments are performed after each study product administration. All Solicited AEs are graded according to the Division of AIDS Table for Grading the Severity of Adult and Pediatric Adverse Events, Corrected Version 2.1, July 2017, except as noted in Section [11.2.2](#).

The Solicited AE assessment period is 3 full days following each study product administration per the assessment schedule shown in [Table 9-3](#). Participants are instructed to record symptoms using a Participant Diary. The site staff and the participant will be in contact after the 3-day Solicited AE assessment period, or sooner if indicated. See the Ab MOP for further details. In general, a participant who self-reports any poststudy product administration reaction greater than mild is seen by a clinician within 48 hours after onset, unless the reaction is improving and/or has completely resolved. Clinic staff will follow new or unresolved Solicited AEs present at day 3 to resolution.

Solicited AEs are reported using CRFs that correspond to the time of assessment in [Table 9-3](#). Solicited AE assessments include assessments of systemic and local symptoms, and study product-related lesions. Events not listed on a CRF, or with an onset after the Solicited AE assessment period (day of study product administration and 3 full days after), or those meeting SAE/Unsolicited AEs requiring expedited reporting according to DAIDS criteria, are recorded on an AE Log.

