#### **6.4.3.1 Solicited AEs**

The number and percentage of participants experiencing solicited AEs, either signs or symptoms, will be tabulated by severity and treatment arm and the percentages displayed graphically by arm. For a given sign or symptom, each participant's solicited AEs will be counted once under the maximum severity for all administration visits. In addition to the individual types of events, the maximum severity of local pain or tenderness, induration or erythema, and of systemic symptoms will be calculated.

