#### 6.4.3.3 Local laboratory values

Boxplots of local laboratory values will be generated for baseline values and for values measured during the course of the study by treatment arm and visit. Each boxplot will show the first quartile, the median, and the third quartile. Outliers (values outside the boxplot) will also be plotted. If appropriate, horizontal lines representing boundaries for abnormal values will be plotted.

For each local laboratory measure, summary statistics will be presented by treatment arm and timepoint, as well as changes from baseline for postenrollment values. In addition, the number (percentage) of participants with local laboratory values recorded as meeting Grade 1 AE criteria or above as specified in the Division of AIDS Table for Grading the Severity of Adult and Pediatric Adverse Events (see Section 9.10) will be tabulated by treatment arm for each postadministration timepoint. Reportable clinical laboratory abnormalities without an associated clinical diagnosis will be included in the tabulation of AEs described above.

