**Table 9-3 Schedule of Solicited AE assessments**

Day	Time	Performed by
0 a	Baseline: before infusion	HVTN CRS clinician
	Early: 25-60 minutes after infusion	HVTN CRS clinician
	Between early assessment and 11:59pm day 0	HVTN CRS clinician or participant
1-3 b	Between 12:00am and 11:59pm on the respective day	HVTN CRS clinician or participant

a Day of infusion

b New or unresolved Solicited AEs present on day 3 are followed until resolution

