### 9.10.1 Assessment of systemic and local symptoms

Systemic symptoms to be assessed as Solicited AEs in this trial include increased body temperature, malaise and/or fatigue, myalgia, headache, chills, arthralgia, nausea, urticaria, non-exertional dyspnea, non-exertional tachycardia (assessed by HVTN CRS staff, not by the participant), generalized pruritus, facial flushing, and unexplained diaphoresis. Local symptoms include pain and/or tenderness at the infusion site. The daily maximum severity reached for each symptom during the assessment period is reported (see Ab MOP).

Body temperature is measured by oral or infrared thermometry. All temperatures must be measured by non-axillary thermometry. This includes temperatures taken in the clinic, as well as temperatures taken by participants during the Solicited AE period.

Temperature is reported in degrees Celsius. If temperature is measured in Fahrenheit, the conversion to Celsius should be documented in the participant's chart note. A measurement is taken once daily during the assessment period and should be repeated if participant is feeling feverish.

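### The solicited AE table makes no use of the clinician baseline taken before each infusion, so systemic symptoms that were already present and merely persist are counted in each arm's percentage

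*Protocol*

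**What the plan says.** **Collection.** Protocol 9.10 requires, for all participants, that "baseline assessments are performed before and Solicited AE assessments are performed after each study product administration". Table 9-3 lists this as a day 0 row, "Baseline: before infusion", performed by a site clinician. The record should be identifiable in the data, because "Solicited AEs are reported using CRFs that correspond to the time of assessment in" Table 9-3.

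**Window and value reported.** "The Solicited AE assessment period is 3 full days following each study product administration". For symptoms, 9.10.1 adds: "The daily maximum severity reached for each symptom during the assessment period is reported".

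**Analysis.** In 6.4.3.1, for a given sign or symptom, each participant's "solicited AEs will be counted once under the maximum severity for all administration visits". The same section adds maxima for local reactions and for systemic symptoms as a group. It does not mention baseline, new onset or worsening. For laboratory values, by contrast, 6.4.3.3 asks for summaries by timepoint "as well as changes from baseline for postenrollment values".

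**Setting.** Solicited signs and symptoms are the first item of primary endpoint 1 (Protocol 5.1). All 24 participants receive product, 12 at each dose, with three infusions each (Table 3-1). The SAP covers pharmacokinetics; its section 1 says it will be updated before the final safety analysis.

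**The concern.** The pre-infusion symptom status is collected at every infusion visit, but the written analysis leaves it out. Fatigue, headache, myalgia and nausea are on the systemic list in 9.10.1, and people have them for many reasons. A participant with Grade 1 headache before an infusion and Grade 1 headache the next day appears in the table exactly as one whose headache began after the infusion.

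Two features make this matter more here. No arm goes without product, so the background frequency cannot be read off a placebo column. And the rule takes the worst grade over three infusions, with a further maximum over the systemic symptoms (13 are listed in 9.10.1), so background has several chances to enter. In an arm of 12, each extra participant moves the reported percentage by 1/12 = 8.3 points.

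**Working it through.** **1. The plan's own safety figures.** Table 6-2 gives score intervals of 0 to 24.2% for 0/12, 1.5 to 35.4% for 1/12 and 4.7 to 44.8% for 2/12. The Wilson score formula returns 0 to 24.25%, 1.49 to 35.39% and 4.7 to 44.8%, so these reproduce. They show how much a single participant matters: going from none to one to two of 12 moves the upper bound from about 24% to 35% to 45%.

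**2. Inputs for the illustration.**
- Participants per arm: 12 (Protocol 6.1).
- Infusions per participant: 3 (Protocol 6.1).
- p, the share of participants who at a given infusion have a symptom before it that is still recorded afterwards. **Assumption**: the documents give no value, so 3%, 5% and 10% are shown.
- No product effect, and no infusion delayed because of the symptom (also assumed).

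**3. Formulas.** If the same people are symptomatic each time, the share counted over three infusions is p. If infusions are independent, it is 1 − (1 − p)³.

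| p | Same people: share (of 12) | Independent: share (of 12) |
|---|---|---|
| 3% | 3% (0.4) | 1 − 0.97³ = 8.7% (1.0) |
| 5% | 5% (0.6) | 1 − 0.95³ = 14.3% (1.7) |
| 10% | 10% (1.2) | 1 − 0.90³ = 27.1% (3.3) |

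A column restricted to symptoms that are new or higher than the same-visit baseline would reduce each of these contributions to zero.

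**4. What such a column leaves in.** Let 10% have a pre-existing persisting symptom at each infusion and let another 5% develop an unrelated one in the days after it, all independent.
- All-grades count: 1 − (0.90 × 0.95)³ = 1 − 0.855³ = 37.5%.
- New-or-higher count: 1 − 0.95³ = 14.3%.

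The pre-existing part goes; the part that starts after infusion stays.

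**The case against.** Several points on the other side are sound.

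- **Attribution.** A reader might infer that background symptoms are being reported as infusion reactions. The documents do not support that: 6.4.3.1 tabulates solicited AEs by severity and arm without causality, and 11.2.2 defines an AE as not necessarily causally related. Counting everything is a conservative convention.
- **The baseline record itself.** A reader might also infer that a symptom which clears after the infusion still counts, because the baseline row sits in Table 9-3. On its natural reading 9.10 says otherwise: it separates baseline from solicited assessments and places the period after administration. A second phrase in 9.10, used to decide what goes to the AE Log, includes the day of administration without splitting it at the infusion. One clarifying clause is therefore worthwhile, but the text does not show that pre-infusion records are counted.
- **Conduct safeguards.** Section 7.3.1 lists pre-infusion symptoms that could mask a reaction among the factors for delaying an infusion, and 9.4 requires an assessment before each one. This keeps some pre-existing symptoms out. Delay is discretionary, so mild symptoms can still be present.
- **Another comparison exists.** The same-visit baseline is not the only internal reference. The two doses are randomised and background should be similar in both, so the dose contrast is informative. What is affected is the level of each arm's percentage.
- **Silence is not a rule.** The safety part of the SAP is still to come, and the antibody manual of operations, cited for assessment details, is not available here. The protocol does not itemise what the baseline assessment contains.
- **Scope.** Infusion-site pain, erythema and induration have little background before an infusion; the point is about systemic symptoms.

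These limit the point without removing it: no written rule separates a persisting symptom from a new one in this table.

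**Conclusion.** The point holds as a reporting gap in a primary safety endpoint, and is not a demonstrated analysis error. As written, 6.4.3.1 includes systemic symptoms that predate an infusion and merely persist, although the data needed to set them apart are collected.

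The size is unknown. At an assumed p of 5%, between 5% and 14% of an arm (0.6 to 1.7 of 12) would be counted with no product effect. This rests on an assumed background rate, on the symptom persisting past the infusion, and on no infusion being delayed under 7.3.1. Gating or quick resolution would make it smaller. The share p also depends on the row: for one named symptom it will be no higher than for the systemic maximum, which pools 13. The larger figures in the table should not be read as an estimate of inflation in this trial.

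The change is worth making because it uses existing data and takes nothing away from the current table.

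**What to change.** In Protocol 6.4.3.1 and in the pending safety section of the SAP:

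1. State that the pre-infusion baseline record is excluded from the maximum severity.
2. Keep the existing all-grades table.
3. Beside it, by arm, give the number and percentage of participants whose post-infusion grade (day 0 early assessment to day 3) is new or higher than the baseline grade at the same visit, for at least one infusion.
4. Label the added column as descriptive, without causal attribution, and note that it does not remove background symptoms arising on days 0 to 3.

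The new column should not be turned into a rule that an event is attributed to an infusion only when it exceeds baseline. That would automatically discount a true reaction occurring at the baseline grade.

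The cost is a sentence or two of text and one extra column per table. No new visits, data collection or change in participant management is needed. Before programming, confirm that the baseline form grades the same symptoms on the same scale as the post-infusion forms, since the protocol does not spell this out.

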**Table 9-3 Schedule of Solicited AE assessments**

Day	Time	Performed by
0 a	Baseline: before infusion	HVTN CRS clinician
	Early: 25-60 minutes after infusion	HVTN CRS clinician
	Between early assessment and 11:59pm day 0	HVTN CRS clinician or participant
1-3 b	Between 12:00am and 11:59pm on the respective day	HVTN CRS clinician or participant

a Day of infusion

b New or unresolved Solicited AEs present on day 3 are followed until resolution

### 9.10.1 Assessment of systemic and local symptoms

Systemic symptoms to be assessed as Solicited AEs in this trial include increased body temperature, malaise and/or fatigue, myalgia, headache, chills, arthralgia, nausea, urticaria, non-exertional dyspnea, non-exertional tachycardia (assessed by HVTN CRS staff, not by the participant), generalized pruritus, facial flushing, and unexplained diaphoresis. Local symptoms include pain and/or tenderness at the infusion site. The daily maximum severity reached for each symptom during the assessment period is reported (see Ab MOP).

Body temperature is measured by oral or infrared thermometry. All temperatures must be measured by non-axillary thermometry. This includes temperatures taken in the clinic, as well as temperatures taken by participants during the Solicited AE period.

Temperature is reported in degrees Celsius. If temperature is measured in Fahrenheit, the conversion to Celsius should be documented in the participant's chart note. A measurement is taken once daily during the assessment period and should be repeated if participant is feeling feverish.

### **9.10.2 Assessment of infusion site**

Typical infusion site reactions are erythema/redness and induration/swelling. The maximum diameter for all infusion/injection site reactions are recorded.

All infusion site reactions are monitored until resolution. Areas with diameters greater than 5 cm are followed daily; otherwise, the frequency of follow-up is based on clinician judgment.

### **9.11 Visit windows and missed visits**

Visit windows are defined in HVTN 128 SSP. For a visit not performed within the window period, a Missed Visit form is completed.

If a participant misses a scheduled visit, the HVTN CRS staff should attempt to bring the participant in as soon as possible to complete the required safety assessments and other procedures. See the HVTN 128 SSP for more details.

If a missed visit required study product administration or if study product administration must be permanently discontinued, please refer to Section [7.3.2](#) and Section [7.3.3](#) for resolution.

### **9.12 Early termination visit**

In the event of early participant termination, site staff should consider if the following assessments are appropriate: a final physical examination, Mucosal sampling acceptability questionnaire, safety contact, clinical laboratory tests (including urine dipstick, CBC with differential, and chemistry panel), pregnancy testing, social impact assessment, and HIV test. See relevant section of the Ab MOP for further details.

### **9.13 Pregnancy**

If a participant becomes pregnant during the course of the study, no more infusions of study product will be given. During pregnancy, no more STI testing, hormonal panel testing, biopsy collections, and mucosal collections will be conducted. Remaining visits and study procedures should be completed unless medically contraindicated or applicable regulations require termination from the study. If the participant terminates from the study prior to the pregnancy outcome, the site should make every effort to keep in touch with the participant in order to ascertain the pregnancy outcome. Pregnancies and pregnancy outcomes will be reported.

If the participant is no longer pregnant (as defined by two consecutive negative tests) or breast-feeding and study product administration and mucosal collections

can be performed within an appropriate visit window, these may resume with unanimous consent of the HVTN 128 PSRT.

See relevant section of the Ab MOP for further details

#### **9.14 HIV infection during the study**

If a participant becomes HIV infected during the course of the study, no additional study product will be administered. In addition, no more STI testing, hormonal panel testing, biopsy collection, and mucosal secretion collections will be conducted. Participants will be encouraged to continue scheduled study visits up to 16 weeks following their last study product administration. Follow-up duration for participants diagnosed with HIV infection may be adjusted in consultation with the CRS investigator and the HVTN 128 PSRT (eg, to avoid interference with participant initiation into HIV treatment). At postinfection follow-up visits, only specimens required for protocol-specified safety laboratory tests, urinalysis, and pregnancy tests will be collected (see [Appendix E](#) and [Appendix F](#)).

See relevant section of the Ab MOP for further details.

## 10 Laboratory

### 10.1 HVTN CRS laboratory procedures

The HVTN 128 Site Lab Instructions and SSPs provide further guidelines for operational issues concerning the clinical and processing laboratories. These documents include guidelines for general specimen collection, special considerations for phlebotomy, specimen labeling, whole blood processing, HIV screening/diagnostic testing, and general screening and safety testing.

Tube types for blood collection are specified in [Appendix D](#). For tests performed locally, the local lab may assign appropriate tube types.

Of note, all assays described below are performed as research assays and are not approved for use in medical care. Results from these assays are not made available to participants or medical professionals to guide treatment decisions.

### 10.2 Total blood volume

Required blood volumes per visit are shown in [Appendix D](#). Not shown is any additional blood volume that would be required if a safety lab needs to be repeated, or if a serum pregnancy test needs to be performed. The additional blood volume would likely be minimal. The total blood volume drawn for each participant will not exceed 500 mL in any 56-day (8-week) period.

### 10.3 VRC07-523LS concentrations

VRC07-523LS levels will be measured in serum, semen, cervicovaginal secretions, rectal secretions, and mucosal tissue lysates prepared from cervical, vaginal, and rectal biopsies collected at the designated timepoints. A quantitative immunoassay will be used to determine the concentration of VRC07-523LS. Ultra-sensitive bead-based analyses enable a broad dynamic range and higher sensitivity (eg, for the anti-idiotypic mAb, 5C9, the lower limit of quantification is approximately 50 pg/mL). The operational sensitivity of the quantitative assays with respect to the various sample specimens will be determined for the clinical grade VRC07-523LS mAb used for this study. VRC07-523LS levels may be normalized relative to total protein and/or total IgG concentrations. Hemoglobin measurements may be used to perform quality control of mucosal secretions.

### 10.4 ADA detection assays

A tiered testing approach will be used to identify and characterize ADAs that may arise. Anti-VRC07-523LS antibody detection assays (screening, confirmatory,

and/or titration) will be performed on serum samples from study participants at indicated timepoints.

### **10.5 ADA functional assay**

A functional ADA assay will be used to characterize any positive activity that is observed in the ADA detection assays. Functional activity will measure a reduction in VRC07-523LS neutralizing activity against a qualified virus in the TZM-bl assay.

### **10.6 Monoclonal antibody reaction assays**

To investigate mAb reactions, serum samples collected after the onset of reaction may be tested to measure levels of certain markers (eg, tryptase, complement components (C3 and C4), and cytokines). ADA detection and functional assays, as described above, may be performed on serum samples taken prior to the study product administration associated with the reaction. Refer to the HVTN 128 SSP for more information.

### **10.7 Exploratory studies**

Samples may be used for other testing and research related to furthering the understanding of HIV immunology, antibody mediated prevention, or vaccines. In addition, samples may be used to perform additional assays to support standardization and validation of existing or newly developed methods.

### **10.8 Specimen storage and other use of specimens**

The HVTN stores specimens from all study participants indefinitely, unless a participant requests that specimens be destroyed or if required by IRB/EC, or RE.

Other use of specimens is defined as studies not covered by the protocol or the informed consent form for the main study (see [Appendix A](#)).

This research may relate to HIV, vaccines, mAbs, the immune system, and other diseases. This could include genetic testing and, potentially, genome-wide studies. This research is done only to the extent authorized in each study site's informed consent form, or as otherwise authorized under applicable law. Other research on specimens will occur only after review and approval by the HVTN, the IRB/EC of the researcher requesting the specimens, and the HVTN CRS's IRBs/ECs/REs if required.

As part of consenting for the study, participants document their initial decision to allow or not allow their specimens to be used in other research, and they may

change their decision at any time. The participant's initial decision about other use of their specimens, and any later change to that decision, is recorded by their HVTN CRS in a Web-based tool that documents their current decisions for other use of their specimens. The HVTN will only allow other research to be done on specimens from participants who allow such use.

HVTN CRSs must notify HVTN Regulatory Affairs if institutional or local governmental requirements pose a conflict with or impose restrictions on specimen storage or other use of specimens.

